5.3.3. Final Analysis

All efficacy analyses and demographic and baseline summaries will be presented by planned treatment group, that is, by either itacitinib or placebo.

5.3.3.1. Full Analysis Set

All subjects who are randomized constitute the FAS.

The FAS will be used for the summary of demographics, baseline characteristics, subject disposition, and analyses of all efficacy data according to intent-to-treat principle.

5.3.3.2. Per Protocol Analysis Set

The per protocol analysis set comprises the subset of subjects in the FAS who are compliant with requirements of the clinical study Protocol, excluding the following:

- Did not receive any dose of itacitinib/placebo after randomization
- Did not meet eligibility criteria
- Had significant deviation(s) from the Protocol in terms of missed study visits, noncompliance with randomized therapy or prohibited concomitant medications
- Subjects later considered as not having aGVHD
- Subjects with MAGIC Criteria Grade 0 or I at Baseline

5.3.4. Safety Analysis Set

The safety analysis set includes subjects randomized into the study who received at least 1 dose of study drug. All safety tables, figures, and listings will be presented by actual treatment group.

5.3.5. Pharmacokinetic and Translational Research Evaluable Analysis Set

Pharmacokinetic and translational research evaluable analysis set includes subjects who receive at least 1 dose of study drug and provide at least 1 plasma sample (1 corresponding PK or translational research measurement) after study drug administration will be considered as potential PK evaluable subjects. The study pharmacokineticist will review data listings of study drug administration and sample records to identify subjects to be excluded from analyses of PK data.

6. BASELINE, EXPOSURE, AND DISPOSITION VARIABLES AND ANALYSES

[Appendix B](#) provides a list of data displays.

In the event that the study terminates at Interim Analysis 1 or 2, the interim safety set will be used in place of the safety analysis set, the interim efficacy set will be used in place of FAS, and any per protocol populations will use subsets of the appropriate interim safety or efficacy set.

6.1. Demographics and Baseline Characteristics, Disease History, Transplant History, Medical History, and Prior Therapies

Demographic and baseline characteristics, disease history, transplant history, medical history, and prior therapies will be summarized for the FAS and listed.

6.1.1. Demographics and Baseline Characteristics

Demographic and baseline characteristics include the following: age, sex, race, ethnicity, weight, height, BMI, BSA, and ECOG performance status.

6.1.2. Hematologic Disease History

Underlying hematologic disease, diagnosis/type of non-malignant and malignant disease, time since initial diagnosis of underlying hematologic disease, and disease risk status will be summarized.

Time since diagnosis of underlying hematologic disease will be calculated as follows:

Time since diagnosis of underlying hematologic disease (days) = Day 1 – date of diagnosis of underlying malignancy + 1.

6.1.3. Allogeneic Hematopoietic Stem Cell Transplant History

Type of allogeneic transplant, time since transplant, donor source, ex vivo T-cell depletion of the allograft (Yes/No), CD34+ positive selection of the allograft (Yes/No), donor CMV type, subject CMV status, HLA matching, HLA score, best response of hematologic disease at the time of transplant, days of diagnosis of aGVHD since transplantation, GVHD organ staging categories, and type of conditioning treatment regimens will be summarized in the FAS by treatment group.

Time since transplant will be calculated as follows:

Time since transplant (days) = Day 1 – date of transplant + 1.

Days of diagnosis of aGVHD since transplantation will be calculated as follows:

Days of diagnosis of aGVHD (days) since transplantation = date of diagnosis of GVHD – date of transplantation + 1.

6.1.4. Medical History

For subjects in the FAS, medical history will be summarized by treatment group. This summation will include the number and percentage of subjects with significant medical history for each body system/organ class as documented on the eCRF.

6.1.5. Prior Anticancer Therapy or Radiotherapy

Number of subjects who received prior anticancer therapy will be summarized for the FAS. Regimen name, component drugs, start and stop dates, purpose of the regimen, best response, reason for discontinuation, and date of relapse/progression will be listed.

Number of subjects who received prior radiation will be summarized for the FAS. Radiotherapy type, body site, start and stop dates, total dose, and best response will be listed.

6.2. Disposition of Subjects

The number and percentage of subjects who were randomized, discontinued study treatment with a primary reason for discontinuation, and withdrew from the study with a primary reason for withdrawal will be summarized for the FAS by treatment group. Subjects entering and discontinuing retreatment will also be summarized.

6.3. Protocol Deviations

Protocol deviations recorded on the eCRF will be presented in the subject data listings. Incidence of different types of protocol deviations will be summarized by treatment group.

6.4. Transfusions Performed On Study or Within 30 Days Before Enrollment

Within 30 days before enrollment, blood component, time since transfusion, quantity, and unit, given AE for transfusion, and the reason for the PRBC/platelet transfusion will be listed. Transfusion performed at any time after randomization will be listed together with those performed within 30 days before enrollment.

6.5. Exposure

For subjects in the safety analysis set, exposure to study drug will be summarized descriptively as follows:

- **Duration of treatment with study drug:**

Duration of treatment (days) = Date of last dose of study drug – Date of first dose of study drug + 1

- **Average daily dose of study drug:**

Average daily dose of study drug (mg/day) = [total actual study drug dose taken (mg)] / [duration of treatment with study drug]

Frequency distribution of itacitinib/placebo duration category (days) will be tabulated by concatenated intervals: Day 1 through Day 28, Day 29 through Day 100, Day 101 through Day 180, and > Day 180.

Similarly, duration of corticosteroid and average daily dose of corticosteroid before EOT as the background therapy will be summarized by treatment group. Frequency distribution of corticosteroid duration category (days) will be tabulated by concatenated intervals.

Frequency distribution of itacitinib/placebo dose modification in the treatment phase (ie, dose decreased due to toxicity, dose increased, dose tapered, dose temporarily interrupted and with previous dose resumed) will be tabulated by concatenated intervals: Day 1 through Day 28, Day 29 through Day 56, Day 57 through Day 84, Day 85 through Day 112, Day 112 through Day 140, Day 141 through Day 168, Day 169 through Day 196, Day 197 through Day 224, Day 225 through Day 252, Day 253 through Day 280, Day 281 through Day 308, Day 381 through Day 336, Day 337 through Day 365, and > Day 365.

In order to summarize corticosteroid use over time in the treatment phase, for days of interest Day X (ie, X = 14, 28, 56, 100, and 180, separately), average corticosteroid dose (mg/day) during the week ending on Day X, relative corticosteroid dose (%) during the week ending on Day X will be summarized by treatment group. Number and percentage of subjects ongoing with itacitinib/placebo and ongoing with corticosteroid on Day X respectively will be summarized by treatment group.

6.6. Study Drug Compliance

For subjects in the safety analysis set, overall compliance (%) for study drug will be calculated for all subjects as follows:

$$\text{Overall compliance (\%)} = 100 \times [\text{total dose actually taken (mg)}] / [\text{total prescribed dose (mg)}]$$

The total prescribed dose is defined as the sum of the doses prescribed by the investigator accounting for dose modifications. The total dose actually taken (mg) is derived by sum of daily dose taken in a specific duration of treatment.

6.7. Prior and Concomitant Medication

Prior medications and concomitant medications will be coded using the WHO Drug Dictionary. For subjects in the safety analysis set, the number and percentage of subjects with prior and concomitant medications will be summarized by WHO drug class and WHO drug term. In the data listing, each medication will be recorded as prior, concomitant, or both prior and concomitant.

The number and percentage of subjects receiving prior GVHD prophylaxis medications will be summarized by treatment group.

The number and percentage of subjects who have ever taken immunosuppressive medications at baseline will be summarized overall and by treatment group. Subjects who took immunosuppressive medications in the 7 days before or on Days 1, 14, 28, 56, 100, and 180 during the treatment phase will be summarized by treatment group.

The number and percentage of subjects undergoing each type of conditioning regimen will be summarized by treatment group.

7. EFFICACY

[Appendix B](#) provides a list of planned data displays.

7.1. General Considerations

In all efficacy analyses, initiation of new, systemic anti-GVHD therapy includes 2 scenarios:

1) initiation of new anti-GVHD therapy including a higher dose of corticosteroid than that used at Day 1 and 2) initiation of new, systemic anti-GVHD therapy when subjects who were treated with placebo in the treatment phase were re-treated with itacitinib in the retreatment phase.

Initiation of new, systemic anti-GVHD therapy will be considered when defining the following:

1) onset of response and 2) loss of response. When defining responder for Day 28 ORR; overall response at Days 14, 56, 100, and 180; and BOR, the onset of response will be censored by initiation of new, systemic anti-GVHD therapy. Responders who did not have GVHD progression or death after response will be censored at the time of either study withdrawal, initiation of new, systemic anti-GVHD therapy, or the date of last assessment of GVHD before or on the cutoff date, whichever is earliest. In the survival analysis of NRM, all subjects in the analysis set in question without a death due to causes other than malignancy relapse will be censored at either study withdrawal, death due to malignancy relapse, or the date of last contact before or on the cutoff date, whichever is earliest.

Duration of response will be calculated for every subject who has a response in the study; DOR will also be summarized for any subgroups of interest.

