## **6.4. Re-Treatment**

For subjects who experience aGVHD recurrence after taper of randomized treatment is completed, investigators have the option to use open-label itacitinib plus corticosteroids for the treatment of recurrent aGVHD irrespective of initial randomized treatment. For the purpose of this Protocol, treatment of recurrent aGVHD with open-label itacitinib plus corticosteroids will be called the re-treatment phase. Subjects entering the re-treatment phase will be required to follow the assessment schedule as outlined in [Table 3](#). Corticosteroid tapering will be performed at the investigator's discretion. Investigators wishing to initiate a taper of itacitinib earlier than Day 180 may do so upon consultation with and approval from the sponsor's medical monitor. Subjects may be re-treated with itacitinib only once. Subjects ending the re-treatment phase will repeat the EOT visit and subsequent safety and survival follow-up visits.

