7.3.2. Duration of Response for Day 28 Responders

The DOR is defined from the time of the first response to the loss of response (ie, either disease progression or death). Responders who did not progress or die after onset of response will be censored, and response will be ended at either study withdrawal, initiation of new anti-GVHD therapy, or last response assessment before or on the cut-off date, whichever is earliest.

Duration of response will be calculated for every responder as well as Day 28 responders.

The DOR for the Day 28 responders will be assessed using the KM method only for subjects who achieve Day 28 response. The KM curves; medians; 1-, 2-, 6-, 12-, 18- and 24-month (equivalently at Days 30, 60, 180, 365, 547, and 730) survival estimates and 95% CIs will be estimated ([Brookmeyer and Crowley 1982](#)). The DOR will be assessed for each treatment group and also by stratum and Day 28 response status.

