7.3.3. Alternative Ways of Calculating Duration of Response for Day 28 Responders

There are 2 other ways of calculating DOR for Day 28 responders:

- **DOR alternate approach 1** – DOR is defined as the interval from Day 28 to either death or initiation of new anti-GVHD therapy, including a higher corticosteroid dose than that administered at Day 1, whichever is earlier.
- **DOR alternate approach 2** – DOR is defined as the interval from Day 28 to the earliest of death, worsening from best response at or after Day 28 in any organ stage, or initiation of new anti-GVHD therapy (including a higher corticosteroid dose than that administered at Day 1).

Summary statistics and KM estimate will be provided by treatment group. Kaplan-Meier plots will also be provided.

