7.4.9. Failure-Free Survival

Failure-free survival is defined as the proportion of subjects who are still alive, have not relapsed of underlying hematologic disease, have not required additional therapy for aGVHD, and have not had signs or symptoms of cGVHD. Subjects without an event of relapse of underlying hematologic disease, death due to relapse, death due to causes other than relapse, initiation of new anti-GVHD therapy, or signs or symptoms of cGVHD will be censored at the date of study withdrawal or the date of last contact before or on the data cutoff date, whichever is earlier. After randomization, the FFS event date will be the first occurrence of one of the following:

- Initiation of anti-GVHD therapy, or
- Relapse/recurrence of underlying hematologic disease, or
- Death due to malignancy relapse, or
- Death due to causes other than malignancy relapse, or
- Signs or symptoms of cGVHD.

Failure free survival will be analyzed according to the randomized treatment group and strata assigned at randomization.

The survival distribution of FFS in each treatment group overall [REDACTED] will be estimated using the KM method, and the KM curves; medians; 1-, 2-, 6-, 12-, 18-, and 24-month (at Days 30, 60, 180, 365, 547, and 730, respectively) survival estimates, and 95% CIs will be presented (Brookmeyer and Crowley 1982). The hazard ratio of treatment relative to placebo overall [REDACTED] will be calculated, along with its 95% CI, using a stratified Cox model. Stratified log-rank test will also be used to test FFS survival curve in the itacitinib group against the placebo group.

Subgroup KM analyses of FFS will also be conducted by Day 28 response status [REDACTED]

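### SAP 7.1 counts open-label itacitinib re-treatment as new anti-GVHD therapy only for subjects first given placebo, which tilts alternate DOR approach 1 towards itacitinib

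*SAP*

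**What the plan says.** **Who can be re-treated.** Under Protocol 6.4, when acute GVHD recurs after the taper of randomised treatment is complete, investigators may "use open-label itacitinib plus corticosteroids for the treatment of recurrent aGVHD irrespective of initial randomized treatment".

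**What counts as new therapy.** SAP 7.1 gives a definition for all efficacy analyses, with two scenarios. The first is a new anti-GVHD therapy, including corticosteroid above the Day 1 dose, and it applies to both arms. The second is "initiation of new, systemic anti-GVHD therapy when subjects who were treated with placebo in the treatment phase were re-treated with itacitinib". There is no matching scenario for subjects first given itacitinib. The section continues: "Initiation of new, systemic anti-GVHD therapy will be considered when defining the following", and names onset of response and loss of response.

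**Where the term is an event.** In SAP 7.3.3, alternate approach 1 reads "DOR is defined as the interval from Day 28 to either death or initiation of new anti-GVHD therapy". Its inline note covers a corticosteroid dose above that of Day 1 and does not mention re-treatment. Alternate approach 2 adds worsening in any organ stage.

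**Where it is not.** The main DOR (SAP 7.3.2) runs to "the loss of response (ie, either disease progression or death"). New therapy is there only a reason for censoring.

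**FFS (SAP 7.4.9).** The definition requires that subjects "have not required additional therapy for aGVHD", and the event list has the bullet "Initiation of anti-GVHD therapy, or". Both are neutral between arms. The censoring sentence instead reads, in part, "initiation of new anti-GVHD therapy, or signs or symptoms of cGVHD will be censored".

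**The concern.** An endpoint event should be scored by the same rule in both arms. Here the rule depends on the randomised arm. Two subjects with the same course (taper completed, GVHD recurs, open-label itacitinib plus corticosteroid at or below the Day 1 dose) are recorded differently: the placebo subject has lost response and the itacitinib subject has not. Randomisation does not protect against this, and the error has one direction.

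At stake is the planned comparison of Kaplan-Meier estimates and plots by arm for alternate DOR approach 1. These are the figures a reader would use to judge how durable Day 28 responses are. A second, smaller matter is that the mixed wording for FFS lets two programmers derive different late FFS results from the same text.

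**Working it through.** The plan gives no DOR, FFS or re-treatment rate, so there is no figure of its own to reproduce. The check has two parts.

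**1. How a re-treated subject is scored** (corticosteroid at or below the Day 1 dose, no other new therapy)

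| Analysis | First given placebo | First given itacitinib |
|---|---|---|
| Alternate DOR approach 1 | Event (scenario 2) | No event |
| Alternate DOR approach 2 | Event | Normally an event, through organ-stage worsening |
| Main DOR | Progression is an event; re-treatment only censors | Progression is an event |
| FFS, 7.4.9 read by itself | Event | Event |
| FFS, 7.1 applied | Event | No event through therapy |

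The corticosteroid restart does not close the gap in approach 1. The Protocol 5.4.3 sentence that treats a restart as progression concerns worsening during the taper. For signs that reappear after a complete taper, the same section only points to re-treatment. In any case approach 1 has no progression event.

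*Timing.* Protocol 5.4.3 lets the taper start at Day 180, with a further step 28 to 56 days later. From 200 mg, through 100 mg, to none, the taper is complete at about Day 208 to Day 236. Re-treatment therefore normally falls after Month 6. An earlier taper needs the medical monitor's approval.

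**2. Assumed size in alternate DOR approach 1**

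Assumptions, none of them from the documents:
- no true difference between arms;
- 75% event-free at Day 180 and 55% at Day 730, with re-treatment counted;
- a share r of each arm's Day 28 responders has re-treatment as first event, spread evenly over Day 208 to Day 730 (522 days);
- no itacitinib re-treatment is caught by scenario 1;
- uncounted subjects go on at the hazard that applies after Day 180.

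Hazard: λ = ln(0.75/0.55)/550 = 0.3102/550 = 0.000564 per day.

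Mean chance that an uncounted subject is still event-free at Day 730: (1 − e^(−522λ))/(522λ) = (1 − 0.745)/0.294 = 0.866.

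False gain at Day 730 = r × 0.866:
- r = 1%: 0.9 points
- r = 2%: 1.7 points
- r = 5%: 4.3 points (59.3% against 55.0%)

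False gain at Day 365: only 157/522 = 0.301 of the re-treatments have happened, and the corresponding mean is (1 − e^(−157λ))/(157λ) = 0.957. The gain is r × 0.301 × 0.957 = 0.3, 0.6 or 1.4 points.

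If scenario 1 catches a share c of itacitinib re-treatments, each figure is multiplied by (1 − c). With c = 0.5 and r = 5%, the Day 730 gain is 2.2 points.

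**Second illustration.** A null simulation used 140 Day 28 responders per arm (the midpoint of 218 × 0.56 = 122 and 218 × 0.72 = 157), follow-up to Day 730 and 2,000 runs per setting. Here the percentage is the share assigned a re-treatment time, not the share with re-treatment as first event.

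| Other events by Day 730 | Re-treated | Event-free, placebo vs itacitinib | Apparent HR |
|---|---|---|---|
| 30% | 2% | 68.6% vs 69.9% | 0.95 |
| 30% | 5% | 66.5% vs 70.1% | 0.88 |
| 50% | 2% | 49.3% vs 50.0% | 0.98 |
| 50% | 5% | 47.6% vs 50.2% | 0.94 |

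With re-treatment counted in both arms, the apparent HR was 0.99 to 1.00 in these settings.

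**FFS, only if 7.1 were applied to it.** Assume 50% FFS at Month 6 and 30% at Month 24, with 218 per arm and no true difference. In simulation, r = 1%, 2% or 5% with full 24-month follow-up gives an apparent HR of about 0.99, 0.97 or 0.93. With staggered follow-up at the final analysis (recruitment dates partly assumed) only about 0.9, 1.8 or 4.5 re-treatments per arm are observed, and the HR is about 0.99, 0.99 or 0.97.

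**The case against.** **The same drug is not new therapy.** For a placebo subject itacitinib is a new agent; for an itacitinib subject it is the assigned one. That is a sensible reason for the wording, and it may suit a censoring rule. It does not justify an event that depends on the arm.

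**Scenario 1 catches some cases.** This stands. Re-treatment includes corticosteroids, and any dose above that of Day 1 counts in both arms. SAP 7.1 also does not say whether restarting corticosteroid at or below the Day 1 dose, after a period without it, is new therapy. The sizes above are therefore upper bounds under their other assumptions.

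**The effect is small.** This largely stands. Re-treatment requires CR or VGPR, at least 8 weeks off corticosteroids, a completed taper, a recurrence and the investigator's choice. With 140 responders per arm, the standard error of the Day 730 difference is about √(2 × 0.55 × 0.45/140) = 5.9 points, which exceeds every gain shown. At the final analysis, due when the last subject reaches Day 180, many subjects will be well short of Day 730, and the gap is smaller at earlier times. Approach 1 has no planned test, and approach 2 and the main DOR are reported beside it.

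**Stronger readings that the text does not support.** A reader might infer that FFS, which has a planned stratified log-rank test and hazard ratio, is biased as well. The documents do not establish this. The 7.4.9 definition and event bullet are neutral between arms, and 7.1 goes on to tie its term to onset and loss of response, which FFS is not. The opposite reading rests on the opening scope of 7.1 and the word *new* in the censoring sentence, so what remains is an ambiguity. A reader might also infer that the primary result is exposed, because 7.1 mentions Day 28 ORR. Re-treatment follows a completed taper that normally starts at Day 180, so it does not bear on Day 28.

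**Conclusion.** The concern holds for alternate DOR approach 1. SAP 7.1 makes re-treatment an event for placebo subjects and, in general, not for itacitinib subjects, and approach 1 has nothing else that captures the recurrence. The direction is fixed, towards itacitinib.

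The size is unknown. Under the stated assumptions the upper bound at Day 730 is about 0.9, 1.7 or 4.3 points for 1%, 2% or 5% re-treated. It falls in proportion to the share that scenario 1 catches, and it is smaller at the follow-up times most subjects will have reached.

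FFS is a secondary wording point: after Month 6 it would be tilted only if 7.1 were applied to it. Month 6 FFS is hardly affected. Day 28 ORR and Month 6 NRM are not affected. Approach 2 is largely protected by its organ-stage worsening event, and in the main DOR new therapy only censors. No multiplicity-controlled alpha is involved (SAP 3.2). The change is worth making because the rule is asymmetric and cheap to repair, not because a main conclusion is at risk.

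**What to change.** - **SAP 7.1:** replace scenario 2 with: entry into the re-treatment phase in either treatment group, dated at Retreatment Day 1.
- **SAP 7.3.3:** state that this definition applies to both alternate approaches, alongside the existing corticosteroid wording.
- **SAP 7.4.9:** use the same term in the event bullet and in the censoring sentence.
- **Reporting:** give the number re-treated per arm beside these results.

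The cost is a few lines of SAP text in three sections and a small change in derivation. No new data are needed: SAP 6.2 already summarises subjects entering re-treatment, and SAP 4.1.4 already defines Retreatment Day 1. The downside is that alternate DOR approach 1, and possibly late FFS, may become slightly less favourable to itacitinib.
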